#### **5.4.1 Randomization Procedures**

The OMS or dental assistant will provide a participant with the randomization assignment after the participant's eligibility is confirmed and his/her consent is obtained. The random assignment will be obtained from the study tablet used by the OMS or dental assistant. The study tablet, which will be programmed by the HP DCC, will (among other things) use randomized treatment assignments from a stratum-specific

(i.e., surgeon-specific) sequence of randomized assignments created as described in the following paragraph. Each surgeon-specific randomization sequence will be loaded into the tablet by the programmer at the HP DCC in such a way that it will be impossible for clinical study personnel, in particular for the OMS or dental assistant to access this sequence or to infer any treatment assignment in the sequence until the moment that assignment is given to a particular participant.

For each stratum (i.e., surgeon), the randomization sequence will be created by the project statistician using custom-written code in the R system (R Foundation for Statistical Computing, Vienna, Austria, <https://www.R-project.org/>), as follows: The sequence will use randomized permuted blocks of size 2 and 4, in each of which the two treatments are present equally often. The R code will first generate a random sequence of block lengths, so that study personnel will never be able to tell which block they are in, and then in each block, the treatment assignments will be randomly permuted, so that each sequence of possible treatments within a block is equally probable.

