### 12.2 Sample Size Considerations

This study's sample size is based on the incidence of TMD pain following 3rd molar removal reported by Huang et al. That observational study reported that among patients undergoing 3rd molar removal, the incidence of jaw joint symptoms lasting more than 1 month was 34.3 per 100 person-years. Among those who did not have a 3rd molar extraction, the rate was 8.8, for a relative risk of 3.8. The incidence of TMD pain reported by patients undergoing surgery was over 30%.

**Primary analysis.** We present a conservative power calculation that assumes we have a single binary outcome (TMD pain yes vs. no) instead of the three measures per person we will collect. The calculations shown below assume two-sided tests and a false positive rate of 5% (alpha = 0.05).

Table 1 shows that 132 patients per group gives 80% power to detect a conservative relative risk of 2.0. To estimate this, we considered a TMD pain incidence of 14% and alpha (type I error) 5%. Table 1's incidences and relative risks are based on data from Huang et al. Note that Huang et al. reported TMD pain incidence over 30%; the current study will have adequate power if the control group's TMD pain incidence is much lower. We will randomize 294 subjects into the study. Assuming 10% loss to follow-up (90% retention), the total sample size will be 264 (132 per group). The assumed retention of 90% is a conservative estimate based on [name] experience in his previous RCT, where 98 of 106 (92%) TMD participants completed their 5-year follow-up visit. Therefore, we anticipate, with patient incentives, that we will obtain 90% or more retention at the 6-month follow-up.

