## 12.4 Final Analysis Plan

All analyses will be by intention-to-treat, with participants included in the group (UC or EC) to which they were randomly assigned.

**Primary analysis.** The primary outcome is incidence of TMD pain within a 6-month follow-up period (a binary dependent variable). The incidence of TMD pain post-surgically will be compared between UC and EC groups. This primary TMD outcome is deemed to have occurred if the patient's self report in the *Patient 1-, 3- and 6-month Follow-up Questionnaires* endorses either or both of the following questions: Pain in jaw with wide opening, or pain in temples, jaw joints or jaw muscles. The primary analysis will include all available follow-up measures (1, 3, and 6 months) for each participant to

estimate incident TMD pain. The UC and EC groups will be compared using an analysis that has the form of logistic regression, but which accounts for correlation of visits within participants using generalized estimating equations (GEE) with each participant being a cluster. The analysis will include group (UC vs. EC), which tests whether the two groups differ in overall frequency of TMD pain; time (1, 3, and 6 months, as a categorical factor); and their interaction (i.e., the time-by-group interaction), which tests for different patterns of change over time in frequency of TMD pain.

In the event of noteworthy amounts of missing data (e.g., patients lost to follow-up or questionnaires not completed), we will check the primary analysis by using standard multiple imputation methods, as implemented in the most recent version of the SAS software (SAS Institute Inc., Cary NC, v. 9.4 or higher), to multiply impute missing data and perform tests. Specifically, we will use SAS's FCS method to create 20 "complete" datasets and otherwise use the defaults in SAS's procedures.

**Secondary analysis.** The primary analysis will not include adjusters, as the randomization should balance the groups. As a check on this, an adjusted version of the primary analysis will include adjusters differing substantially between the two randomized groups, selected from the list of potential adjusters given below (see "Potential Adjusters", below).

Other secondary analyses are as follows:

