1. The incidence of TMD pain, as measured with the validated *TMD Pain Screener Questionnaire* (*binary dependent variable*), will be compared between the UC and EC groups within a 6-month follow-up period based on patients' self report in the *Patient 1-, 3- and 6-month Follow-up Questionnaire*. These analyses will have the same form as the primary analysis.
2. TMD pain intensity, as measured with the validated Characteristic Pain Intensity (CPI) within a 6-month follow-up period (treated as a continuous measure), will be compared between the UC and EC groups based on patients' self report in the *Patient 1-, 3- and 6-month Follow-up Questionnaire*. Unadjusted and adjusted analyses (using adjusters selected as described above) will be performed using GEE as in the primary analysis.
3. Baseline characteristics, specifically all of the potential adjusters listed below (see "Potential Adjusters", below), will be compared between the UC and EC groups. Analyses will use t-tests, possibly after transforming the measure because it has a skewed distribution, Chi-squared test and Fisher's Exact Test.

4. The UC and EC groups will be compared for TMJ noise, pain characteristics (e.g., location in temple or jaw, and occurrence with wide opening of mouth) and change in jaw pain since it started, within a 6-month follow-up period based on patients' self report in the *Patient 1-, 3- and 6-month Follow-up Questionnaire*. These analyses will have the same form as the primary analysis.
5. A descriptive summary of the experiences of surgeons and dental assistants with the new device at mid-way through recruitment of patients and at the end of recruitment based on their self report in the *Doctor Questionnaire Regarding Use of the Device* and *Dental Assistant Questionnaire Regarding Use of the Device*, respectively,

All analyses will use SAS version 9.4 or later (SAS Institute Inc., Cary, NC). All tests will use a significance threshold of 0.05 (2-tailed).

Potential adjusters: The following characteristics will be compared between the UC and EC groups as potential adjusters:

- Patient demographics
- Baseline patient-reported symptoms (e.g., TMJ noise, pain or discomfort around wisdom teeth, frequency of oral habits as measured with the Oral Behaviors Checklist (OBC), and health status; see *Patient Baseline Questionnaire*).

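### Balance is not the reason to leave baseline covariates out of the primary GEE: pre-specified adjustment could modestly improve precision if they are prognostic

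*Combined protocol and SAP*

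**What the plan says.** Section 12.4 (Final Analysis Plan) specifies a logistic GEE, clustered by participant, with three terms: group, visit and their interaction. No baseline variable enters. The only reason given is "The primary analysis will not include adjusters, as the randomization should balance the groups".

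An adjusted version is planned as a secondary check. Its covariates are those found to differ substantially between the arms, drawn from a list of potential adjusters. The analysis of characteristic pain intensity (CPI) also has an adjusted version that uses the same selection. The list covers demographics, patient-reported baseline symptoms, surgeon findings and procedural characteristics. Among the patient-reported items it names "frequency of oral habits as measured with the Oral Behaviors Checklist (OBC), and health status", together with TMJ noise and discomfort around the wisdom teeth. Sex is not named; it could only come in under demographics.

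Section 12.2 sizes the trial without covariates: "Table 1 shows that 132 patients per group gives 80% power to detect a conservative relative risk of 2.0".

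**The concern.** The stated reason answers a question about chance imbalance. The main gain from covariates in a randomized trial is precision. A baseline variable that predicts the outcome leaves residual variation in an unadjusted comparison even if its distribution is identical in the two arms.

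The secondary check does not fill the gap. Because it selects on observed difference, a strong predictor that happens to be balanced is left out, while a weak one that happens to differ is included.

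The data needed are already planned. Sections 4, 5.3 and 7.2 place the patient baseline forms before randomization, and Section 8.1 says the baseline questionnaire covers TMJ noise, wisdom-tooth pain and oral habits. At stake is a modest amount of power in a trial whose own calculation gives 80%.

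**Working it through.** **Inputs from the documents.** Two-sided alpha 0.05, 80% power, relative risk 2.0, incidence 14%, 132 per group, 10% loss and 294 randomized (Section 12.2). Allocation is 1:1, from "randomized permuted blocks of size 2 and 4, in each of which the two treatments are present equally often" (Section 5.4.1).

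**Assumptions.** The number, distribution and odds ratios of the covariates, and the share of outcome variance they explain (R²). The documents give none of these.

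**1. The plan's own figure.** With 14% as the lower-risk arm and 28% as the higher, the mean is 0.21 and

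n = [1.96·√(2·0.21·0.79) + 0.8416·√(0.14·0.86 + 0.28·0.72)]² / 0.14² = (1.1290 + 0.4776)² / 0.0196 = 131.7, so 132 per group.

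Power at 132 per group is 80.1%. Then 264/0.9 = 293.3, so 294. The stated sample size reproduces with no covariates.

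**2. Simulated power with and without adjustment.** Logistic regression, one binary outcome per patient, 132 per arm, marginal risks held at 28% and 14%, three covariates (binary, standard normal, binary), 4,000 trials per row.

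| Binary prevalences | Odds ratios (normal covariate per SD) | Unadjusted | Adjusted | Gain (points) |
|---|---|---|---|---|
| 55%, 30% | 1 / 1 / 1 | 79.8% | 80.2% | 0.4 (noise) |
| 55%, 30% | 1.5 / 1.3 / 1.5 | 79.6% | 80.6% | 1.0 |
| 55%, 30% | 2 / 1.5 / 2 | 79.6% | 81.6% | 2.0 |
| 55%, 30% | 2.5 / 2 / 3 | 80.9% | 85.7% | 4.8 |
| 50%, 20% | 1.5 / 1.3 / 1.5 | 79.4% | 80.9% | 1.5 |
| 50%, 20% | 2 / 1.5 / 2 | 79.7% | 82.8% | 3.1 |
| 50%, 20% | 2.5 / 1.8 / 2.5 | 79.6% | 83.8% | 4.2 |

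With 12,000 trials per setting, the last three rows give gains of 1.0, 2.4 and 4.1 points (Monte Carlo standard error of the paired difference 0.18 to 0.26). These are the better estimates for those settings.

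**3. Type I error.** With 28% in both arms and the first four covariate settings, rejection rates were 4.4% to 5.5% unadjusted and 4.7% to 5.7% adjusted.

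**4. Cross-check by variance reduction.** Effective n per group = 132/(1 − R²).

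| R² | Effective n | Power |
|---|---|---|
| 0.02 | 134.7 | 80.9% |
| 0.05 | 138.9 | 82.1% |
| 0.07 | 141.9 | 82.9% |
| 0.10 | 146.7 | 84.1% |
| 0.15 | 155.3 | 86.1% |

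The second to fourth simulated settings correspond to R² of about 0.03, 0.07 and 0.15. The approximation runs somewhat above the simulation (2.8 against 2.0 points at 0.07; 6.0 against 4.8 at 0.15), so the simulated gains are the ones to rely on.

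**Limit of the check.** These runs use one outcome per patient. The planned three-visit GEE, the CPI model and the standardized risks were not simulated.

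**The case against.** The strongest reply is that nothing here is wrong. A pre-specified unadjusted comparison in a randomized trial is valid, its simulated type I error is close to 5%, and the planned power never relied on covariates. Section 12.2 also calls its calculation conservative because it counts one outcome instead of three. The usual-care rate matters at least as much as the weak to moderate covariates: at 132 per group and a relative risk of 2, a 30% usual-care rate gives about 83.5% power and a 34% rate about 89%. All of this stands, and it is why the point is minor.

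A reader might infer that sex, oral habits and baseline symptoms would certainly supply power. The documents do not support that. They never say that any of these predicts the outcome, and they list them only as potential adjusters. Section 5.2 also excludes patients reporting TMD pain in the past 3 months, which removes the most obvious baseline symptom, though not TMJ noise, oral habits or wisdom-tooth discomfort.

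A reader might also infer that the gain is free. It is not quite. Covariates in a logistic model change the target from a marginal to a conditional odds ratio, so a standardization step has to be written for a repeated-measures model. Missing covariates should be a small problem: under Sections 5.5.1 and 7.2, declining essential baseline data counts as withdrawal, and Section 16.2 says the data system blocks missing entries.

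The planned adjusted check is a partial answer only, because it selects by imbalance.

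**Conclusion.** The point holds as a small efficiency improvement to a valid analysis. The balance argument does not justify leaving out pre-specified prognostic covariates, and the secondary check does not reliably recover the precision given up. At 28% against 14% with 132 per arm, the gain would be roughly 1 to 2.5 points of power for weak to moderate covariates and about 4 for strong ones. It is nil, with no visible penalty, if they are not prognostic. These sizes rest entirely on assumed covariate strengths and on a single binary outcome.

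It would be going too far to say that the omission biases the result, inflates type I error or leaves the trial underpowered by its own calculation: the stated 132 per group and 80% reproduce without any covariate.

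**What to change.** Before any unblinded look at the data, amend Section 12.4 as follows:

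- Name a short fixed list for the primary GEE and the CPI model, used whatever the observed balance: Oral Behaviors Checklist score, patient-reported baseline TMJ noise, baseline wisdom-tooth pain, and sex once it is confirmed that the demographics form collects it. At the design rates about 0.28·132 + 0.14·132 = 55 patients would have an event, so the list should stay short. State the form of each covariate.
- Exclude anything recorded after assignment. Section 8.1 has the surgeon's questionnaire completed after surgery, so surgery duration, extraction difficulty and procedural items should not enter.
- Report standardized (marginal) risks by arm with their difference and ratio. Specify the step for the repeated-measures model: whether risks are given per visit or averaged over visits, and how standard errors respect clustering by participant. If the CPI model uses an identity link, it does not have the odds-ratio problem.
- Keep the present unadjusted model as a sensitivity analysis.

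How the surgeon strata enter the model is a separate question. The cost is SAP wording and some programming for standardization; no new data and no change in trial conduct.

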## 5.2 Subject Exclusion Criteria

**Patients** who meet any of the following criteria will be excluded from participation in this study:

- In the past 3 months, reports the presence of TMD pain in their temples, jaw joints or jaw muscles;
- Contraindication(s) for moderate/deep sedation or general anesthesia;
- Any condition or situation the surgeon determines that would prevent the patient from participating in this study;
- Inability to understand study procedures or provide consent in English;
- Device does not fit mandible;
- Supernumerary 3rd molars present.

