#### Patients – Baseline:

- Patients who have consented to study participation will provide contact information for study follow-up, demographic information and a baseline questionnaire, which will assess: 1) presence of any TMJ noise in past 3 months, 2) presence of any jaw or temple pain, 3) current pain or discomfort associated with their wisdom teeth, 3) Presence of any oral habits, and 4) and general health status.
- Patient will be randomized to: 1) Usual Care (UC) with a bite block and hand support of the jaw, or 2) Experimental Care (EC) with a bite block and the Restful Jaw device to support the jaw.
- The device will be positioned (EC group only) and placed prior to the surgical procedure.

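### Secondary item 4 in section 12.4 compares TMJ noise without a prespecified term for noise present before surgery; to the extent that noise persists, the contrast is diluted and power is lost

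*Combined protocol and SAP*

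**What the plan says.** Section 12.4, secondary item 4: "The UC and EC groups will be compared for TMJ noise, pain characteristics" and change in jaw pain, using the three follow-up questionnaires. It adds: "These analyses will have the same form as the primary analysis". That form is a logistic GEE model with group, time and group-by-time, and section 12.4 says the primary analysis carries no adjusters.

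Other relevant places:

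- **Eligibility.** Section 5.2 excludes a patient who, in the past 3 months, "reports the presence of TMD pain in their temples, jaw joints or jaw muscles". No criterion concerns TMJ noise.
- **Baseline data.** Section 8.1 (Patients – Baseline) has the patient report "presence of any TMJ noise in past 3 months". Section 4 places this questionnaire before surgery, and section 7.2 lists it ahead of the random assignment.
- **Follow-up data.** Section 8.1 (Patient – Follow-up) describes the item simply as whether TMJ noise is present.
- **Adjustment.** Section 12.4 provides that "an adjusted version of the primary analysis will include adjusters differing substantially between the two randomized groups". Baseline TMJ noise is on the candidate list twice, as a patient report and as a surgeon finding, and item 3 compares it between arms. An adjusted analysis is also stated for pain intensity (item 2). None is stated for item 4.

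**The concern.** For pain, the entry exclusion makes follow-up pain close to new-onset pain, so an unadjusted model is workable. Item 4 carries that model over to a symptom with no such exclusion. A patient who had a clicking joint before surgery and still has it at 1 month counts as a case in either arm. Such patients add events to both arms without separating them, so the ratio moves toward 1 and the test loses power.

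The adjuster rule does not address this. It is triggered by imbalance between arms, whereas dilution occurs even when baseline noise is perfectly balanced. Reading item 4's reference to the primary form as including the adjusted version would still leave adjustment dependent on imbalance. At stake is a real reduction in new TMJ noise being reported as no difference.

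**Working it through.** **1. The plan's own figure.** Section 12.2 states: "Table 1 shows that 132 patients per group gives 80% power to detect a conservative relative risk of 2.0". It uses two-sided alpha 0.05 and an incidence of 14%. With 14% in one arm and 28% in the other, mean 0.21:

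n = [1.96·√(2·0.21·0.79) + 0.8416·√(0.14·0.86 + 0.28·0.72)]² / 0.14² = (1.129 + 0.478)² / 0.0196 ≈ 131.7, so 132 per arm, with power 80.1%. Then 264 / 0.90 = 293.3, so 294. Both stated figures reproduce, with 14% as the lower-risk arm.

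**2. Inputs for TMJ noise.** The documents give no rate for baseline noise, its persistence or new-onset noise. Assumed:

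- new-onset noise p = 28% UC and 14% EC (borrowed from the pain contrast)
- share with baseline noise b = 10% to 40%
- share of those still reporting noise s = 100%, then 80%, equal in both arms
- one time point, 132 per arm

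**3. Formula.** Observed risk per arm = b·s + (1 − b)·p. The risk difference is therefore (1 − b) times the new-onset difference. Example, b = 20%, s = 100%: UC 0.20 + 0.80·0.28 = 0.424; EC 0.20 + 0.80·0.14 = 0.312; RR = 1.36.

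**4. Results, s = 100%.** Power is for the two-proportion test with pooled variance. The last column is a simulated test stratified on baseline noise (4,000 runs), standing in for a covariate in the GEE model.

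| b | UC vs EC | RR | OR | Power as planned | Noise-free patients per arm | Power, noise-free only | Power, stratified |
|---|---|---|---|---|---|---|---|
| 0% | 28.0% vs 14.0% | 2.00 | 2.39 | 80% | 132 | 80% | – |
| 10% | 35.2% vs 22.6% | 1.56 | 1.86 | 62% | 119 | 76% | 77% |
| 20% | 42.4% vs 31.2% | 1.36 | 1.62 | 47% | 106 | 71% | 70% |
| 30% | 49.6% vs 39.8% | 1.25 | 1.49 | 36% | 92 | 65% | 65% |
| 40% | 56.8% vs 48.4% | 1.17 | 1.40 | 28% | 79 | 58% | 58% |

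Among noise-free patients the RR stays at 2.00 throughout.

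**5. Sensitivity.**

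- With s = 80%, the planned analysis gives RR 1.61, 1.41, 1.29 and 1.21, with power 64%, 49%, 37% and 28%. Stratified power is about 71%, 61%, 50% and 40%. The stratified advantage shrinks but remains.
- With new-onset risks of 14% vs 7%, power without baseline noise is 46%. For b = 10% to 40% and s = 100%, it falls to 25% to 10% as planned, against 42% to 30% in noise-free patients. Levels change; the ordering does not.

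**The case against.** Four points can be made for the plan.

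1. **Baseline noise is not ignored.** It is recorded by patient and surgeon, compared between arms and listed twice as a candidate adjuster. This stands: a reader might infer that the plan takes no account of it, and that would be wrong. The gap is that its use is conditional and not stated for item 4.
2. **The all-patient comparison is legitimate.** Secondary objective 3 speaks of comparing TMJ noise, not its incidence, and randomisation makes the comparison valid. This stands. A reader might infer bias between arms, or that the outcome cannot answer its question; neither follows.
3. **Existing noise may respond to jaw support.** One might argue that noise present before surgery is fixed background. The documents do not say so, and section 2.1 notes that dental procedures may aggravate existing subclinical symptoms. If the device reduced persistence, restriction could discard information. Illustration: b = 20%, persistence 80% UC vs 60% EC, new onset 20% vs 10%. Power is about 60% for all patients unadjusted, 53% restricted and 73% stratified. With equal persistence of 80%, unadjusted power is about 30% and stratified just over 40%. So this weakens restriction as the main analysis, but not adjustment.
4. **The follow-up wording is unseen.** Case report forms are separate from the protocol. If the item asks only about noise new since surgery, the dilution largely disappears. Section 8.1 gives no sign of such a qualifier, but the form should be checked.

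**Conclusion.** The point holds as a loss of sensitivity in one secondary outcome. Item 4 neither limits TMJ noise to new onset nor commits to a baseline-noise term, and the imbalance-driven adjuster rule cannot repair dilution that exists under balance.

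Under the assumptions above with full persistence, a true RR of 2.0 would appear as 1.56 to 1.17 for baseline noise of 10% to 40%, and power would be 62% to 28%, against 76% to 58% when baseline noise is handled. These are illustrations: prevalence, persistence and new-onset risk are all assumed, and the three-visit GEE model will not give exactly the single-visit power. With no baseline noise there is no loss.

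A reader might extend the point to the primary pain outcome. The documents do not support that, because recent TMD pain is an exclusion.

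**What to change.** In section 12.4, item 4:

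- **Main TMJ-noise analysis:** keep all randomised patients and always include patient-reported baseline TMJ noise (past 3 months, Patient Baseline Questionnaire) as a covariate, whether or not the arms differ.
- **Supporting analysis:** prespecify new-onset noise among patients without baseline noise. The subgroup is defined before randomisation, so the comparison stays randomised, but it answers a narrower question in fewer patients.
- **Source of the covariate:** use the patient's report. By section 8.1 the surgeon's questionnaire is completed after the operation, and by section 5.4.2 the surgeon knows the assignment.

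State also whether the follow-up item asks about any noise or only noise since surgery. The adjusted odds ratio is conditional on baseline noise and should be labelled so. The cost is SAP wording: the baseline item is already collected, and no patients, visits or forms are added. Settling this before outcome data are seen avoids a post hoc choice of model.

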**Patient – Follow-up:**

- At 1, 3, and 6 months post-baseline, patients will complete follow-up questionnaires via an online questionnaire, which will assess: 1) presence of TMJ noise, 2) presence of jaw or temple pain including frequency, duration, intensity, 3) pain-related disability; 4) factors that increase or decrease their pain, and 4) whether the jaw pain is getting better, worse or staying the same.

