## 12 STATISTICAL CONSIDERATIONS

### 12.1 Study Hypotheses

The risk of developing TMD pain in patients undergoing 3rd molars removal in the EC group will be statistically lower within the 6-month follow-up interval than in the UC group.

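### The change-in-jaw-pain item, analysed as the plan words it, compares the arms only among patients who developed pain after randomization; define it for all patients or report it descriptively

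*Combined protocol and SAP*

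**What the plan says.** Secondary outcome 3 (section 3.2.2) and secondary analysis item 4 (section 12.4) list "change in jaw pain since it started, within a 6-month follow-up period" beside TMJ noise and pain characteristics. For the whole group section 12.4 states: "These analyses will have the same form as the primary analysis". That form is "an analysis that has the form of logistic regression", with GEE for repeated visits and terms for group, time and their interaction, applied to a yes/no outcome. Every test in section 12.4 is two-tailed at 0.05, and only item 5, the clinicians' experience, is called descriptive.

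Section 8.1 (Patient – Follow-up) describes the item as "whether the jaw pain is getting better, worse or staying the same".

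Three further statements bear on it:

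- Section 5.2 excludes a patient who "In the past 3 months, reports the presence of TMD pain in their temples, jaw joints or jaw muscles".
- Section 12.1 hypothesizes: "The risk of developing TMD pain in patients undergoing 3rd molars removal in the EC group will be statistically lower".
- Section 12.4 states: "All analyses will be by intention-to-treat, with participants included in the group (UC or EC) to which they were randomly assigned".

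Sections 3.1, 3.2.2 and 12.4 give no dichotomy, no ordinal model and no code for a patient without jaw pain.

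**The concern.** Pain that never started cannot have changed since it started. Recent TMD pain is an exclusion, so the pain being rated arises almost entirely after randomization, and its occurrence is what the device is meant to alter. Restricting the comparison to patients with pain selects on an effect of treatment. The two pain subsets need not be alike even though the randomized arms are.

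If the device mainly prevents pain that would have improved anyway, the remaining EC cases are the stubborn ones, and EC shows a lower improving rate with no patient harmed. If it mainly prevents stubborn pain, EC looks better on this item than any effect on the course of pain would justify. In both cases the patients the device spared are left out of the count.

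Three answers also have to be turned into something a binary model can take. If the rule is left open until the data are seen, the choice of split is post hoc.

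**Working it through.** **The plan's own figure.** The documents give no number for this endpoint, so the reproducible figure is the primary sample size in section 12.2. Inputs: calculations that "assume two-sided tests and a false positive rate of 5" percent, 80% power, 1:1 allocation, incidence 14%, relative risk 2.0.

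With p1 = 0.28, p2 = 0.14 and mean 0.21, using pooled variance and no continuity correction:

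n = [1.960·√(2·0.21·0.79) + 0.842·√(0.28·0.72 + 0.14·0.86)]² / 0.14² = 132 per group (power 80.1%).

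264/0.90 rounds up to 294. All twelve cells of Table 1 reproduce within one patient when the tabled incidence is taken as the lower rate. The 28% is therefore derived (14% × 2.0), not stated. Taking 14% as the higher rate (14% against 7%) would need 300 per group.

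**Patients with pain to rate**, using TMD pain incidence as a stand-in for jaw pain and one rating per patient:

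- 14% as the EC rate: UC 132 × 0.28 = 37; EC 132 × 0.14 = 18. Together about 55 of 264 (21%).
- 14% as the UC rate: UC 132 × 0.14 = 18; EC 132 × 0.07 = 9.

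**Illustration of the selection.** Take UC 28% and EC 14%. Assume 14% of patients have pain under either arm (not preventable), 14% have pain only under UC (preventable), and the device does not change the course of pain. Let a and b be the proportions improving among non-preventable and preventable cases. The documents give neither, so both are assumptions.

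- Improving among patients with pain: UC = (a + b)/2; EC = a.
- Pain not improving among all patients: UC = 0.14(1 − a) + 0.14(1 − b); EC = 0.14(1 − a).

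The simulation columns come from 200,000 trials per row with 132 per arm, comparing proportions among patients with pain.

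| a / b | Improving, UC vs EC | Odds ratio (EC:UC) | EC estimate worse | Nominally significant: EC worse / EC better | Pain not improving, all patients, UC vs EC |
|---|---|---|---|---|---|
| 50% / 50% | 50% vs 50% | 1.00 | 50% | 2.6% / 2.6% | 14.0% vs 7.0% |
| 40% / 60% | 50% vs 40% | 0.67 | 75% | 10% / 0.4% | 14.0% vs 8.4% |
| 30% / 70% | 50% vs 30% | 0.43 | 92% | 29% / under 0.1% | 14.0% vs 9.8% |
| 60% / 40% | 50% vs 60% | 1.50 | 24% | 0.4% / 10% | 14.0% vs 5.6% |

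For the third row: EC:UC odds ratio (0.3/0.7)/(0.5/0.5) = 0.43; UC not improving 0.098 + 0.042 = 0.140; EC 0.14 × 0.7 = 0.098.

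The pain-only comparison moves either way although the device does nothing to the course of pain. It is unbiased only when a = b. The all-patient figure favours EC in every row, as it should when the device prevents pain and harms no one.

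**The case against.** **The questionnaires are not in the documents.** Section 8.1 is a one-line summary, and case report forms are listed among the supplemental materials, outside the protocol. A no-pain answer cannot be excluded. This stands, and it limits the point to the item as the plan words it. It does not close the gap: a fourth answer would still need a coding rule for a binary model. Section 16.2 says missing entries block progress, so pain-free patients must either skip the item or be given an answer, and the plan does not say which.

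**A reader might infer that the stated model cannot be fitted.** The documents do not support that. Item 2 already carries GEE over to a continuous score, so the shared form in item 4 could be stretched to an ordinal logit, and a suitable dichotomy fits the binary model directly. The fault is an undefined outcome and population.

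**The intention-to-treat sentence favours an all-patient reading.** It does, but it settles only the arm in which a patient is counted. It supplies no value where none exists. Multiple imputation is specified only as a check on the primary analysis.

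**The numbers are hypothetical.** They are: the improvement splits have no source in the documents, 28% is derived, and the item is rated at three visits rather than once. Under the milder 40%/60% split, a nominally significant result against the device appears in only about 10% of simulated trials.

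**The consequence is small.** One component of a secondary item is affected, and no stopping, sizing or success decision rests on it. This stands.

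**Conclusion.** The concern holds for this one component. Analysed as worded, the test conditions on pain that arises after randomization and that the device is meant to reduce. It is not a randomized comparison and could wrongly favour or disfavour the device. The conclusion rests on the item having no value for pain-free patients, which is inferred from its wording. Bias arises if prevented and remaining pain run different courses, which the documents neither assert nor rule out.

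On the planning rates about a fifth of evaluable patients would contribute (37 UC and 18 EC), or about half as many (18 and 9) if 14% is the UC rate. The 50% against 30% contrast shows what can happen and is not a forecast.

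A reader might conclude that the sign of the result reflects case mix and not the device, or that an effective device will look worse. Neither follows: the device may also change the course of pain, the distortion can run in either direction, and it vanishes when both kinds of pain behave alike. The primary analysis and the other secondary items, including pain location, which can be coded no for a pain-free patient, are unaffected.

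**What to change.** In section 3.2.2 item 3 and section 12.4 item 4:

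1. Define the tested outcome at each visit as *jaw pain present and not improving* (same or worse), yes or no, for every randomized patient with follow-up at that visit. A patient free of jaw pain at that visit counts as no. This fits the stated logistic GEE.
2. Report the better/same/worse split among patients with pain by arm, without a test, and label it as not a randomized comparison.

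A four-level ordinal outcome (no pain, better, same, worse) with a cumulative-logit GEE is an optional alternative. It adds a proportional-odds assumption and would be dominated by the no-pain level, about 79% of patients at the planning rates (100% − 21%), so it would largely repeat the primary comparison.

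The cost is wording in two sections and minor programming. Pain presence and the change item are already collected at each follow-up, so no new data are needed. The rule should be fixed before any outcome data by arm are seen.
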